7.2.2. Vital Signs

Vital signs (Blood Pressure, Pulse Rate, Body temperature and Respiratory rate) will be recorded at all the visits and at any time at the discretion of the Investigator. Systolic BP will be measured after the subject has rested for at least 5 minutes in supine position.

7.2.3. General and Systemic Evaluation

A general and systemic examination will be conducted by a physician at each study visit and includes (at a minimum) a thorough examination of Head, Neck, Eye, Ear, Nose, Throat, Skin & Appendages, Renal, Cardiovascular, Pulmonary, Reproductive, Endocrine, Gastrointestinal, Nervous System, Musculoskeletal, Peripheral Vascular system and Psychiatric.

7.2.4. Adverse events

All reported adverse events and serious adverse events will be recorded and reported as per section Adverse Events.

8.0 ADVERSE EVENTS

8.1. Definitions

The following International Conference on Harmonization of Technical Requirements for Registration of Pharmaceuticals for Human Use (ICH) AE definitions apply to this study:

Adverse Event: An AE means any untoward medical occurrence associated with the use of a drug in humans, whether or not considered drug related.

Serious Adverse Event: An SAE, experience or reaction, is any untoward medical occurrence (whether considered to be related to study drug or not) that at any dose:

- Results in death.
- Is life-threatening (the patient is at a risk of death at the time of the event; it does not refer to an event which hypothetically might have caused death if it were more severe).
- Requires in patient hospitalization or prolongation of existing hospitalization: Hospital admissions and/or surgical operations planned before or during a study are not considered AEs if the illness or disease existed before the patient is enrolled in the study, provided that it did not deteriorate in an unexpected way during the study.
- Results in persistent or significant incapacity or substantial disruption of the ability to conduct normal life functions.
- Results in a congenital abnormality/birth defect.
- Other: Medically significant events, which do not meet any of the criteria above, but may jeopardize the patient and may require medical or surgical intervention to prevent one of the other serious outcomes listed in the definition above. Examples of such events are blood dyscrasias (e.g., neutropenia or anemia requiring blood transfusion, etc.) or convulsions that do not result in hospitalization.

An adverse drug reaction (ADR) is defined as all noxious and unintended responses to a medicinal product related to any dose.

Unexpected adverse event or unexpected suspected adverse reaction: An adverse event or suspected adverse reaction is considered “unexpected” if it is not listed in the investigator brochure or is not listed at the specificity or severity that has been observed; or, if an investigator brochure is not required or available, is not consistent with the risk information described in the general investigational plan or elsewhere in the current application, as amended. For example, under this definition, hepatic necrosis would be unexpected (by virtue of greater severity) if the investigator brochure referred only to elevated hepatic enzymes or hepatitis. Similarly, cerebral thromboembolism and cerebral vasculitis would be unexpected (by virtue of greater specificity) if the investigator brochure listed only cerebral vascular accidents. “Unexpected,” as used in this definition, also refers to adverse events or suspected adverse reactions that are mentioned in

the investigator brochure as occurring with a class of drugs or as anticipated from the pharmacological properties of the drug, but are not specifically mentioned as occurring with the particular drug under investigation.

Each and every unexpected adverse event observed during study will be medically managed Investigator team at site and followed up till resolution or stabilization. All the details of UAE will be captured in AE pages of CRF/ eCRF. If UAE qualifies for any of the SAE criteria the timelines for recording and reporting the UAE will be as per SAE timelines.

Each AE is to be evaluated for duration, severity, seriousness, and causal relationship to the investigational drug. The action taken and the outcome must also be recorded.

8.2. Severity

The severity of unsolicited AEs will be characterized as “mild”, “moderate”, or “severe” according to the following definitions:

Table VIII: Severity of adverse reactions

Mild	Moderate	Severe
Events are usually transient and do not interfere with the subject’s daily activities.	Events introduce a low level of inconvenience or concern to the subject and may interfere with daily activities.	Events interrupt the subject’s usual daily activity.

8.3. Relationship

The causal relationship between the study drug and the AE has to be characterized as related, unrelated, unlikely, possible, probable, or unknown (unable to judge).

Table IX: Causality Assessment

Related	Events can be classified as “related” when there is a direct possibility that the study drug cause AE.
Unrelated	Events can be classified as “unrelated” if there is not a reasonable possibility that the study drug caused the AE.
Unlikely	An “unlikely” relationship suggests that only a remote connection exists between the study drug and the reported AE. Other conditions, including chronic illness, progression or expression of the disease state or reaction to concomitant medication, appear to explain the reported AE.
Possible	A “possible” relationship suggests that the association of the AE with

	the study drug is unknown; however, the AE is not reasonably supported by other conditions.
Probable	A “probable” relationship suggests that a reasonable temporal sequence of the AE with drug administration exists and, in the Investigator’s clinical judgment, it is likely that a causal relationship exists between the drug administration and the AE, and other conditions (concurrent illness, progression or expression of disease state or concomitant medication reactions) do not appear to explain the AE.
Unknown	All efforts should be made to classify the AE according to the above categories. The category “unknown” (unable to judge) may be used only if the causality is not assessable, e.g., because of insufficient evidence, conflicting evidence, conflicting data, or poor documentation.

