Inhaled corticosteroids should be used with caution, if at all, in patients with active or quiescent tuberculosis infection of the respiratory tract; untreated systemic fungal, bacterial, parasitic or viral infections; or ocular herpes simplex.

Paradoxical Bronchospasm

Inhaled corticosteroids may produce inhalation induced bronchospasm with an immediate increase in wheezing after dosing that may be life-threatening. If inhalation induced bronchospasm occurs following dosing with QVAR, it should be treated immediately with an inhaled, short-acting bronchodilator. Treatment with QVAR should be discontinued and alternate therapy instituted.

Immediate Hypersensitivity Reactions

Hypersensitivity reactions, such as urticaria, angioedema, rash, and bronchospasm, may occur after administration of QVAR. Discontinue QVAR if such reactions occur.

Hypercorticism and Adrenal Suppression

QVAR will often help control asthma symptoms with less suppression of HPA function than therapeutically equivalent oral doses of prednisone. Since beclomethasone dipropionate is absorbed into the circulation and can be systemically active at higher doses, the beneficial effects of QVAR in minimizing HPA dysfunction may be expected only when recommended dosages are not exceeded and individual patients are titrated to the lowest effective dose.

Because of the possibility of systemic absorption of inhaled corticosteroids, patients treated with QVAR should be observed carefully for any evidence of systemic corticosteroid effects. Particular care should be taken in observing patients postoperatively or during periods of stress for evidence of inadequate adrenal response.

It is possible that systemic corticosteroid effects such as hypercorticism and adrenal suppression (including adrenal crisis) may appear in a small number of patients, particularly when beclomethasone dipropionate is administered at higher than recommended doses over prolonged periods of time. If such effects occur, the dosage of QVAR should be reduced slowly, consistent with accepted procedures for reducing systemic corticosteroids and for management of asthma symptoms.

Effects on Growth

Orally inhaled corticosteroids, including QVAR, may cause a reduction in growth velocity when administered to pediatric patients. Monitor the growth of pediatric patients receiving QVAR

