10.5. Safety Analysis

Summary of adverse events, Treatment Emergent Adverse Events, Serious adverse event, events leading to discontinuation and treatment related adverse events will be presented for each arm.

Summary of Vital signs and Laboratory parameter values at relevant time-points as well as change from baseline will be presented. Summary of use of various concomitant medications will be presented. By Subject data listings will be presented for all safety data captured on CRF/eCRF.

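### Table IX is not an ordered or mutually exclusive causality scale, and an event with both a plausible drug cause and a plausible other cause has no clear category

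*Protocol*

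**What the plan says.** Protocol section 8.3 asks for each adverse event to be placed in one of six categories, defined in Table IX:

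- *Related* applies "when there is a direct possibility that the study drug cause AE".
- *Unrelated* applies when there is no reasonable possibility of a drug cause.
- *Unlikely* has two elements. Such a "relationship suggests that only a remote connection exists between the study drug and the reported AE", and in addition "Other conditions, including chronic illness, progression or expression of the disease state or reaction to concomitant medication, appear to explain the reported AE".
- *Possible* applies when the association of the event with "the study drug is unknown; however, the AE is not reasonably supported by other conditions".
- *Probable* needs a reasonable temporal sequence, an investigator's judgement that a causal link is likely, and that other conditions ("concurrent illness, progression or expression of disease state or concomitant medication reactions) do not appear to explain the AE").
- *Unknown* is a residual category that "may be used only if the causality is not assessable, e.g., because of insufficient evidence, conflicting evidence, conflicting data, or poor documentation".

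The ratings are used in section 10.5, where "events leading to discontinuation and treatment related adverse events will be presented for each arm". That section does not say which of the six categories count as treatment related. Section 8.4 also requires the investigator's preliminary causal classification in the information supplied for a serious adverse event.

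**The concern.** A causality scale has to do two things. Its categories should run from weaker to stronger evidence of a drug cause, and each event should have one natural place. The middle category normally takes events that the drug could have caused but that something else could also have caused. Table IX closes its middle category to exactly those events.

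This matters more here than in many trials. Every subject has asthma, which section 1.0 describes through recurrent wheezing, breathlessness, chest tightness and coughing. The same section warns for the drug class that "Inhaled corticosteroids may produce inhalation induced bronchospasm with an immediate increase in wheezing after dosing that may be life-threatening", and it names coughing among the events more frequent on the reference product than on placebo. Events with two plausible causes are therefore to be expected. Safety and tolerability of the test product is the only secondary objective (section 2.2), and investigators at about 40 centres would each have to decide how to use the table.

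**Working it through.** No arithmetic applies, because no rate, sample size or margin in the protocol bears on the point. The check sets the Table IX definitions side by side and then tries to place one event.

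**Step 1: what each category demands.**

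| Category | Required link to the drug | Requirement on other causes |
|---|---|---|
| Unrelated | no reasonable possibility | none stated |
| Unlikely | only remote | other conditions appear to explain the event |
| Possible | association unknown | event not reasonably supported by other conditions |
| Probable | reasonable timing, causal link judged likely | other conditions do not appear to explain the event |
| Related | a direct possibility | none stated |
| Unknown | not assessable | none stated |

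**Step 2: is the scale ordered?**

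- On other causes, *possible* is at least as strict as *probable*. A condition can lend reasonable support to an event without appearing to explain it. An event in that position is barred from *possible* but not, on this criterion, from *probable*.
- *Related* has no timing requirement, no judgement of likelihood and no condition on other causes. As worded it is weaker than *probable*.

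**Step 3: are the categories mutually exclusive?** An event with good timing, a likely causal link and no other explanation meets *probable*. It also meets *related*, since a likely cause is at least a possible one. The table gives no rule for choosing between them.

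**Step 4: place an event with two plausible causes.** Take wheeze after a dose in a subject whose asthma could also produce it.

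- *Unrelated* does not fit, because there is a reasonable possibility of a drug cause.
- *Unlikely* does not fit on its first element, because the drug connection is not merely remote.
- *Possible* is excluded, because asthma reasonably supports the event.
- *Probable* is excluded if asthma appears to explain the event, and otherwise needs the causal link to be judged likely.
- *Related* is open, but only because its wording is loose.
- *Unknown* is open only if the investigator regards causality as not assessable, for example because the evidence conflicts. The table asks that all efforts be made to use another category first.

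One investigator could reasonably choose *related*, a second *unknown*, and a third *unlikely* because it is the category that expressly mentions expression of the disease. The same difficulty arises for cough, and for pharyngitis where an upper respiratory infection is also a candidate cause.

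**Step 5: which outputs depend on the ratings?** Section 8.4 has all adverse events recorded whatever their causality. Of the summaries listed in section 10.5, only the treatment-related one uses Table IX. Adverse events, treatment-emergent events, serious events and events leading to discontinuation do not.

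**The case against.** The strongest reply is that the damage is small. The all-causality tables carry the main safety comparison and are untouched. Investigators are blinded (section 9.5) and use one scale in every arm, so no bias in favour of one product is to be expected. Reporting of serious events within 24 hours is triggered by seriousness, not causality. All of this stands and limits the point to one descriptive summary and to the causality field on individual reports.

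It can also be said that the choice of categories that count as treatment related belongs in the SAP. That is fair, and its absence from section 10.5 is not a fault. But a mapping made at analysis cannot repair ratings already made on unclear definitions.

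Three stronger readings are tempting, and the protocol supports none of them:

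- A reader might infer that any event asthma could also explain is pushed into *unlikely*. That category also needs a merely remote drug connection, and its other conditions must appear to explain the event, not merely be able to. Wheeze immediately after dosing is not a remote connection.
- A reader might infer an undercount of treatment-related events. The loose wording of *related* could equally raise the count, and the protocol does not map the categories to treatment related.
- A reader might apply the adverse-event rates in section 1.0 to the 620 subjects planned per active arm to size the problem. Those rates include events whether or not considered drug related, so the product would count events, not misclassified ones. Several also run below placebo in the column for 80 to 160 mcg daily: rhinitis 8% against 9%, upper respiratory infection 7% against 11%, and increased asthma symptoms 2% against 18%. Only pharyngitis (6% against 4%) and oral symptoms (3% against 2%) among the likely examples exceed it.

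**Conclusion.** The concern holds as a defect in the wording of Table IX. The categories are neither ordered nor mutually exclusive, and an event with both a plausible drug cause and a plausible alternative cause has no clear place. The per-arm treatment-related summary cannot be relied on for such events. The direction of error is unsettled and its size cannot be derived from the protocol.

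This rests on two assumptions: that sites apply Table IX as written, and that events with two plausible causes occur, which the protocol's own descriptions of asthma and of the drug make likely. It does not show that a difference between test and reference would be hidden in the trial, since the all-causality summaries would still show it.

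**What to change.** Reword Table IX in section 8.3 and the matching CRF guidance:

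- *Possible*: the event follows study drug in a reasonable temporal sequence, but could also be explained by the disease, a concomitant medication or another condition.
- *Unlikely*: the connection with study drug is remote and another cause is more likely.
- *Related*: drop the category, or define it as requiring stronger evidence than *probable*.

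Which categories are counted as treatment related in section 10.5 may be left to the SAP.

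The cost is a change to protocol and CRF-guidance wording. Treatment-related counts may change in all arms. Events already rated under the present text would keep unclear ratings unless investigators reassess them while still blinded.

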8.4. Reporting of Adverse Events

Adverse Events

All AEs that occur in a subject from the time subject signs the ICF for the study, regardless of severity, causality, and whether or not they occurred during the course of the trial are to be recorded in the appropriate AE pages (either ‘serious’ or ‘non-serious’) in the CRFs/ eCRFs. Investigator shall complete all the details requested including dates of onset, severity, action taken, treatment measures, outcome, and relationship to study drug, and any other treatment measures undertaken. Each event should be recorded separately.

At the End of study visit, subjects will be queried regarding any AEs that have occurred since the Treatment visit. Subjects will be asked to volunteer information with a non-leading question such as, “How have you felt since your last visit?” Study center personnel will then record all pertinent information in the subject’s CRF/ eCRF.

Serious Adverse Events

Within 24 hours of learning of any AE that meets one of the criteria for an SAE, Investigator must report the event as per Appendix XI to sponsor/AXIS, Licensing authority and ethics committee. Sponsor/AXIS with Investigator shall send SAE report after due analysis to Licensing authority, ethics committee and head of the institute where trial is being conducted within 14 days. Investigator shall ensure that ethics committee shall send SAE report and its opinion on financial compensation within 30 days to the licensing authority. Sponsor shall pay compensation as per the orders by licensing authority within 30 days of receipt of orders from licensing authority. A follow up report shall be sent to sponsor/AXIS, Licensing authority, and

head of the institute where trial is conducted within 14 days of the occurrence of SAE which shall include outcome and treatment provided. If, during follow-up, any non-serious AE worsens and eventually meets the criteria for an SAE, that AE should be recorded as a new SAE.

The study center must transmit the SAE form to the SAE [contact] or email to [contact]. SAE form (as per appendix XI compliance) shall be sent to licensing authority and Ethics committee which accorded approval at the site. Even if an initial report is made aware by the site personnel telephonically to the sponsor or AXIS representative, an SAE form completed with all available details must still be faxed within 24 hours of knowledge of the event at the study center.

Supplemental information shall be submitted as soon as available and may include laboratory results, radiology reports, progress notes, hospital admission and emergency room notes, treatments administered for the events, holding and observation notes, discharge summaries, autopsy reports, and death certificates.

The Investigator is expected to take all therapeutic measures necessary for resolution of the SAE. Any medications or procedures necessary for treatment of the SAE must be recorded on the appropriate pages of the subject's CRF/eCRF and SAE form. All SAEs are to be followed up by the study staff until resolution or until the SAE is deemed stable. The Sponsor or AXIS may contact the study center to solicit additional information or follow up on the event.

The original CRF/ eCRF pages should be returned immediately to the CRF/eCRF binder. The information must include at least the following:

- Name, address, and telephone number of the reporting Investigator.
- Study drug and Protocol Number.
- Subject identification number, initials, sex, and date of birth.
- Description of the SAE, measures taken, and outcome.
- Preliminary classification of causal relationship by the Investigator.

Additional follow-up information should be completed on an SAE follow-up form with a copy sent to the Sponsor /AXIS and the original placed in the SAE section of the CRF/ eCRF binder.

In the case of fatal or life-threatening events please also immediately telephone the Safety Surveillance and Reporting Unit:

Country	Name/Phone number:
India	[name] Associate Vice President – Clinical Research AXIS Clinicals Limited. [name] Direct : [name] [contact] [contact] e-mail : [contact] [contact]
India	[name]. [name] Medical Manager AXIS Clinicals Limited [name], India. [contact] [contact] Mob: [name] Email: [contact]

In case of an accidental overdose, the study center personnel will take necessary measures to bring the subject to a stable state and will report overdose to AXIS Clinicals.

8.5. Follow-up of Adverse Events

Any AEs observed after signing the ICF till study completion will be followed up to resolution. Resolution means that the subject has returned to a baseline state of health or the PI does not expect any further deterioration of the condition.

8.6. Asthma exacerbations

Asthma exacerbations

Asthma exacerbations are episodes characterized by a progressive increase in symptoms of shortness of breath, cough, wheezing or chest tightness and progressive decrease in lung function, i.e. they represent a change from the subject's usual status that is sufficient to require a change in treatment.

* Exacerbations are identified as events characterized by a change from the subject's previous status.

Severe asthma exacerbations

Severe asthma exacerbations are defined as events that require urgent action on the part of the subject and physician to prevent a serious outcome, such as hospitalization or death from asthma.

Management of asthma exacerbations

All asthma exacerbations would be managed by stepwise approach as suggested by the Global initiative for asthma 2018 strategy for asthma management & prevention. Please see the Appendix -6 for more details.

